## Outcome Measures

Main Outcome Measure: 7-day point prevalence abstinence at the end of 12 weeks. This outcome will be measured by self-report of abstinence for the past 7 days, and confirmed using a plasma cotinine measurement of  $\leq 15$  ng/ml

## Secondary Outcome Measures:

1) Fagerstrom Test of Nicotine Dependence (FTND). The FTND will be used to assess physical

dependence severity in participants [40].

2) Expired Carbon Monoxide (CO) Measurements. Expired CO measurements will be regularly taken as a biological confirmation of recent smoking.

3) Cigarettes per day. The Timeline Follow-Back (TLFB) will be used to determine daily self-reported cigarette consumption [42].

4) Minnesota Nicotine Withdrawal Scale (MNWS). The MNWS will be used to assess tobacco withdrawal symptoms [50].

5) Tiffany Questionnaire of Smoking Urges (T-QSU). The T-QSU will be used to assess symptoms of craving/urges for tobacco [51].

6) Point prevalence abstinence at end of 4 weeks: This outcome will be measured by self-report of abstinence for the past 7 days and confirmed using a plasma cotinine measurement of <15 ng/ml.

7) Prolonged abstinence from end of treatment (Week 12) to end of follow up (Week 26). This outcome will be measured by self-report of continuous abstinence since the last visit (at Week 12) and confirmed using a plasma measurement of <15 ng/ml.

8) Prolonged abstinence with 2-week grace period at end of follow up (Week 26). This outcome will be measured by self-report of continuous abstinence since Week 4 and confirmed using a plasma measurement of <15 ng/ml.

9) Continuous abstinence at 6 months: This outcome will be measured by self-report of continuous abstinence since the target quit day (Week 2) and confirmed using a plasma measurement of <15 ng/ml.

The FTND, T-QSU and MNWS will be administered weekly for the first month (i.e. 4 weeks) and subsequently at 8, 12 and 26 weeks.

In the case that a participant declines blood draws, urine will be collected instead for the quantification of cotinine levels.

### **Study Monitoring and Access to Study Documents**

The PI/ QI will permit trial-related monitoring, audits, REB review, and/or regulatory inspections, by providing direct access to source data/documents. This will be mentioned in the Informed Consent Form. Monitoring will be conducted according to the study monitoring plan.

### **Ethical Considerations**

This study is approved by CAMH REB.

### **Risks and Inconveniences**

Blood Collection: Blood collection may cause some bruising and discomfort at the site of needle stick, and rarely, a small infection at the skin puncture site. These risks are minimized by using proper techniques.

Varenicline: Current prescribing practice recommends varenicline be administered at 0.5mg once daily for 3 days, 0.5mg twice daily for 4-7 days followed by 1mg twice daily for the remainder of treatment. According to the varenicline product monograph, the most common side effect of varenicline is nausea, which is dependant on dose. Approximately 30% of subjects treated with 1mg varenicline reported nausea while 16% of subjects reported these symptoms at a 0.5mg

dose. However, this symptom was typically described as being mild to moderate in severity and transient causing only 3% of subjects to discontinued treatment prematurely because of this adverse effect. Other common adverse effects associated with varenicline treatment include sleep disturbances, constipation, and vomiting. There are reassuring data concerning the mental health side effects of varenicline [4]. However, we will monitor suicidality by the Columbia-Suicide Severity Rating Scale. Should any subject begin experiencing significant changes in their mood or behavior, we will ask them to discontinue the medication and contact the study physician or if they cannot contact the study physician, to attend their local emergency room for treatment.

rTMS: When the stimulation is applied to the head, the machine yields a sound. To minimize any inconvenience, ear plugs will be offered to subjects to mute the sound. At certain positions on the head, the stimulation may cause eyes to blink or a brief contraction of the scalp, neck, trunk or upper arm muscles. While these contractions may be annoying, they should not be painful. Some people may experience a mild headache or shoulder stiffness after testing but these symptoms will usually go away in 24 hours. Typically, 1-2 doses (325 mg) of acetaminophen (i.e. "Tylenol") should help to rid these symptoms.

Very rarely, rTMS has been reported to cause seizures. For example, there have approximately been a total of 10 reported seizures when safety guidelines are followed out of thousands of treated patients. However, patients with epilepsy and/or patients with stroke may be more vulnerable to potential seizures. Safety guidelines that minimize seizure risk will be followed. We intend to follow these guidelines and control stimulation so it is well below the maximum limits of the safety guidelines. To our knowledge, no seizures have been reported when stimulation is kept within these safety guidelines. Magnetic brain stimulation (rTMS) has been used on thousands of individuals in the United States, Canada and Europe over several years without any serious problems. That said, the study investigator (or delegate) will be available during rTMS sessions, and will immediately assess and treat any emerging side effects.

Questionnaires: There are no risks associated with the questionnaires, except possibly fatigue. Breaks will be provided as required.

Benefit to participants: Should the dual treatment approach for nicotine dependence be successful, subjects will directly benefit from participation in the study.

### **Study Documentation**

Investigators will retain a participant identification code list if they need to contact participants after the study. This list will contain the complete name, identification number, address, phone number and email of all participants and will be held confidentially at the investigator's site after completion of the study.

### **REDCap**

REDCap will be used as an electronic data capture tool for some questionnaires. If used for this purpose, data collected in REDCap will be considered as source.

REDCap may also be used as a survey for recruitment purposes. For recruitment, the survey will be a stand alone site where participants will answer preliminary questions to determine eligibility. To gain access to the survey, participants will respond to our advertisement by email or telephone. Staff will reply to them with a unique Study ID that the participant will use to gain access to the survey. No PHI will be stored in the same Project as the Survey. At the end of the survey participants will give consent to be contacted and they will be directed to a stand-alone Project with their telephone number and name. The only link between the Survey and Telephone number Project will be a unique Screening ID.

### **Archiving of Study Documentation**

Study data and other essential documents will be retained in a secure setting by the investigators for a period of 15 years as required by current regulations.

### **Confidentiality**

All personal study participant data collected and processed for the purposes of this study will be managed by the investigators and their research staff with adequate precautions to ensure the confidentiality of this data, and in accordance with applicable national and local laws and regulations on personal data protection. The Ethics Committees approving this research, monitors and Health Canada will be granted direct access to all source documents for verification of clinical trial procedures and/or data, without violating the confidentiality of the participants, to the extent permitted by the law and regulations. In any presentation of study results (at meetings or in publications), participant identity will remain confidential.

### **Participant Safety and Adverse Events**

The occurrence of adverse events resulting from varenicline treatment and/or rTMS intervention is a possibility, particularly as we are not excluding various co-morbid disorders. However, in a previous trial completed by our team, we demonstrated the safe use of varenicline in smokers presenting with co-morbid alcohol dependence. Similarly, large recent meta-analyses also reveal the safety of varenicline in smokers with various psychiatric diagnoses [41]. Regardless, possible side effects will be monitored on a regular basis (weekly) during the medication phase. Moreover, we will follow current guidelines for the safe use of both varenicline and deep rTMS, including the exclusion of individuals with any known absolute contraindications to either of these treatments.

The Qualified Investigator (QI) will ensure patient safety. Potential safety concerns and associated solutions will be discussed at regular study meetings. Since this study involves both a pharmacological (varenicline) and device (rTMS with H-coil) intervention, the QI (along with any medical professionals delegated by the QI) will monitor, treat and follow-up on any emerging side/adverse effects. In the event of AEs, the QI will determine severity of the event along with any causal association to the study interventions.

#### **Additional Safety Procedures:**

1. Participants will be provided with the QI contact information with an available pager number for 24-hr contact, in case of any unexpected side effects.
2. If necessary, the participants will be transferred home via taxi.

### **Adverse Events Reporting**

Every adverse event and observed device deficiency will be recorded. AEs will be assessed at each study visit. Study staff will question the subject directly asking: how they are feeling and how have they been feeling since last visit. All AEs, whether reported by the subject or observed by study staff/investigators, will be recorded on the AE log along with a brief description, start date/resolution date and any action taken. Symptoms related to smoking cessation will not be recorded as AEs. The AE log will be initialed by the QI, who will make the determination on relationship of the AE to the investigational device/study procedures.

Serious adverse events and device deficiencies meeting Health Canada's mandatory problem reporting requirements (Part 3, Medical Devices for Investigational Testing Involving Human Subjects) will be reported to Health Canada within the reporting time periods required by Health Canada and/or to REB in accordance with REB's local reporting requirements and timelines.

### **Termination of the Study**

Reasons for withdrawing individual subjects from the study may include one or more of the following:

- 1) Failure to continue to meet inclusion criteria;
- 2) Severe rTMS side effects;
- 3) Major protocol violation;
- 4) Subject lost to follow-up;
- 5) Withdrawal of consent;
- 6) Pregnancy
- 7) The subject missed more than 3 days of TMS treatment during the treatment trial period (not including holiday closures or due to COVID)

Notably, any subject may be discontinued from the study at the discretion of the Qualified Investigator if it is deemed to be in the best interest of the subject.

When participants are prematurely withdrawn they will be replaced by a new participant until the total recruitment aims are met or until the trial is stopped. Replacement will be according to the inclusion and exclusion criteria above and will follow the same procedure as for the original participants. Data collected until the time of withdrawal may be used in analyses.

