Recruitment for the study may also be initiated by members of the *Circle of Care* who are treating the potential study participant. These individuals will not obtain consent but they may identify potential research participants and obtain verbal permission for a member of the research team to approach and discuss the study with them. Potential participants who provide assent to be contacted by a member of the research team will then be contacted by a member of the research team who will engage them in the informed consent process if they are agreeable to proceed as such.

Additionally, as part of the CLEARR (Clinical Engagement and Research Recruitment) initiative, a delegated Research Coordinator under the supervision of a CLEARR team recruiting clinician and accountable to the Manager of Research Practice will identify potential participants and notify the research team and the client's clinician about the potential eligibility to participate in the study. The clinician will then ask the client for assent to meet with a study team member to discuss details and participation in the study. Only clients who agree to this process will be approached.

The delegated research Coordinator will access personal health information (PHI) in I-CARE in order to determine eligibility of CAMH participants to participate in the research study. No PHI except MRN will be collected for this purpose and this information will be kept in a secure locked location.

The aforementioned recruitment strategies are in line with our aim to enroll a representative sample of smokers. This is in contrast to more traditional smoking cessation clinical trials, wherein the majority of smokers are often excluded, thereby jeopardizing the generalizability of the data [5]. Our exclusion criteria may be regarded as less restrictive for this purpose. Nicotine dependence will be determined via testing/ measurements stated in the "Screening Assessment" section below.

Interventions and Procedures: Potential participants will undergo a telephone pre-screen to determine initial eligibility. Participants may also complete this screening electronically, through REDCap (see REDCap section). They will subsequently be invited to an in-person Screening Assessment to confirm final eligibility to participate.

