In addition to the screening assessment, there will be 30 study visits. The first visit (study start day) will correspond to the 1st varenicline dose and the 1st rTMS session. There will be 4 consecutive weeks of rTMS (20 sessions). Weekly follow-up visits will occur for the 12 weeks of the trial and a final visit will occur at week 26. The TLFB, SAFTEE, concomitant medication log and Adverse Event log will be administered/ updated at every visit. CO measurements will also be taken at every visit. Regular pregnancy testing for females will occur throughout the study. Selective questionnaires (described below in Outcome Measures) will also be administered at study sessions. Urine drug testing will be conducted as required. There will be a total of 4 blood draws (including the screening session). Cotinine blood samples will not be analyzed upon collection. The clinical lab will process the samples and the study staff will pick up the samples and store them in a -20°C freezer. Analysis will be done in batches of 30 or more samples.

*Varenicline Treatment:*

All participants will receive varenicline pharmacotherapy, beginning at Week 1, for a total duration of 3 months (12 weeks). A target quit date for all participants will be set for Day 15. The varenicline dosage schedule will be that standard for smoking cessation. It will consist of 0.5 mg tablet once a day for the first three days (day 1 – day 3), followed by four days of 0.5 mg BID (i.e. twice a day: AM and PM; day 4-7). The target daily dose of 2 mg (1 mg BID, i.e. twice

a day: AM and PM) will begin on Week 2 (day 8) and extend until the end of treatment. Subjects will be advised to orally consume the tablet with food and water. Notably, we may use 1 mg daily if 2 mg daily is not well tolerated. The study medication will be dispensed weekly by the CAMH pharmacy. Compliance will be assessed through reported missed doses at weekly visits (see *Follow-up Visits* section below).

*rTMS:*

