**Subject Eligibility Criteria**

*Inclusion criteria:*

- 1)** Age 18-65;
- 2)** Nicotine dependent as assessed by DSM-V;
- 3)** Reported daily cigarette consumption  $\geq 10$  and expired carbon monoxide (CO) measurement of  $\geq 10$  ppm;
- 4)** Fagerstrom Test of Nicotine Dependence (FTND)  $\geq 4$ ;
- 5)** Reported motivation to quit within 30 days as assessed using the Contemplation Ladder score of  $\geq 7$ .

*Exclusion criteria:*

- 1)** Reported smoking abstinence in the 3 months preceding screening visit;
- 2)** Current use of other smoking cessation aids;
- 3)** Allergy and/or contraindication to varenicline or rTMS;
- 4)** Pregnancy, trying to become pregnant or breastfeeding;
- 5)** Current or recent history of cardiovascular or cerebrovascular disease and/or current hypertension;
- 6)** Current or historical evidence of suicidal behavior;
- 7)** Serious current or personal history of medical condition/disease (neurological disorders, brain lesions, multiple sclerosis, head trauma, loss of consciousness, hearing loss, etc.);
- 8)** Current, personal history or family history of seizures;
- 9)** Cognitive impairment as defined as a Mini Mental State Examination (MMSE) score  $<24$ ;
- 10)** Concomitant use of medication that lowers seizure threshold.

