## Data Analysis

Descriptive statistics will be used to compare groups (Sham, rTMS) at baseline on main clinical and demographic variables. Fisher's Exact and Mann-Whitney U test will be used for categorical and continuous variables, respectively. Subjects with missing values in the primary outcome (abstinence at 4, 12 or 26 weeks) will be compared with completers on baseline characteristics, to help in the understanding of the reasons for missing values, if at least 10 subjects (20%) are found to be missing. Mixed effect logistic regression that uses abstinence at 4, 12 and 26 weeks as dependent variables will be adjusted to the data, with groups and categorical time (4, 12 and 26 weeks) specified as fixed effect, and subject intercepts as random effects. Baseline variables correlated with missingness and/or known to be associated with the outcome will be added as covariates with focus on model parsimony (not to include many covariates) due to small sample size. The primary hypothesis will be tested using a contrast that compares abstinence at week 12 in the logit scale. Similarly, abstinence will also be compared at weeks 4 and 26 as part of our secondary objectives. Mixed effect models that uses maximum likelihood estimation accounts for missingness in the dependent variable by using all available information in the estimation, under the MAR assumption (Missing At Random – the values of a data points are not associated with the missing status of the data point after accounting for relevant covariates) [49]. Other measures related to our secondary objectives (e.g., FTND, CO, TLFB, etc.) will also be analyzed using linear mixed or generalized mixed models, depending on the nature of the outcome of interest. Graphs will be used to explore the data, the models assumptions (for example, residual plots), as well as model results (for example, estimated means plot). Due to small sample, effect sizes with 95% confidence intervals as well as standardized effect sizes will be reported.

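### Could the withdrawal rule on continuing to meet inclusion criteria remove participants from the trial because they stopped smoking?

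*Combined protocol and SAP*

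**What the plan says.** Termination of the Study opens its list with "Reasons for withdrawing individual subjects from the study may include one or more of the following", and the first of seven items is "Failure to continue to meet inclusion criteria". It then says "When participants are prematurely withdrawn they will be replaced by a new participant until the total recruitment aims are met", and "Data collected until the time of withdrawal may be used in analyses". It does not mention collecting outcomes after withdrawal.

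Under Subject Eligibility Criteria, the third inclusion criterion begins "Reported daily cigarette consumption". It sets a minimum of 10 a day together with an expired CO of at least 10 ppm, and its wording names no time of assessment. Outcome Measures defines the primary outcome as seven days of self-reported abstinence at the end of Week 12, confirmed by plasma cotinine.

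Study Design (Interventions and Procedures) says that participants attend an in-person screening assessment "to confirm final eligibility to participate". On follow-up, Total Number of Study Visits states that "CO measurements will also be taken at every visit".

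**The concern.** The word for continuing in the withdrawal reason carries the inclusion criteria past entry. A participant who has not smoked for seven days reports zero cigarettes a day and so fails the third criterion. No section exempts abstainers. CO and the cigarette diary are recorded at every visit, so the failure would be visible in the data.

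If the reason were used this way, Week 12 and Week 26 abstinence would be missing because of abstinence itself. The planned mixed logistic model assumes data missing at random given abstinence at Weeks 4, 12 and 26 and selected baseline variables ("Baseline variables correlated with missingness and/or known to be associated with the outcome will be added as covariates"). The CO and diary readings between those weeks, which would trigger the withdrawal, are not in the model. The week-12 contrast could then be biased if withdrawal of quitters differed between arms, and replacement would fill the places with new participants.

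**Working it through.** **1. The literal conflict.** Seven-day abstinence means 0 cigarettes a day; 0 is below 10; the third criterion fails. The wording does conflict.

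**2. What the other sections require.**

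| Section | Content | Bearing |
|---|---|---|
| Termination of the Study | Reasons that may lead to withdrawal | Optional, not automatic |
| Interventions and Procedures; Screening Assessment and Consent | Final eligibility set at screening, where the instruments behind the smoking, dependence and motivation criteria are given | Criteria are used at entry |
| Summary of Events | SCID and Contemplation Ladder at visit 1 only | Two of the five criteria have no scheduled re-check |
| Secondary Outcome Measures | CO, cigarettes per day and FTND are outcomes | Repeat readings measure effect; none is described as an eligibility check |
| Varenicline Treatment; rTMS; Follow-up Visits | Quit date Day 15, two further weeks of rTMS, drug and counselling to Week 12 | Quitters are meant to stay on treatment |
| Secondary Outcome Measures, items 7 to 9 | Three prolonged or continuous abstinence outcomes at Week 26 | Abstainers are meant to stay in follow-up |

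**3. The plan's sample size.** Inputs from Sample Size and Power Calculation: 40% on varenicline, a 30-point difference (so 70%), power 0.80, alpha 0.05 (two-sided assumed).

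n = [1.96 × √(2 × 0.55 × 0.45) + 0.8416 × √(0.24 + 0.21)]² / 0.30² = (1.379 + 0.565)² / 0.09 ≈ 42 per arm.

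This matches the stated 42 and confirms that the difference is absolute.

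**4. The literal reading against the attrition allowance.** The plan recruits 30 per arm to obtain 50 completers, an allowance of 60 − 50 = 10 losses (16.7%). Expected Week 12 abstainers among 60 recruits: 0.40 × 30 + 0.70 × 30 = 12 + 21 = 33 (55%). On 25 per arm: 10 + 17.5 = 27.5 of 50, again 55%. The sham arm's 12 alone exceeds the whole allowance of 10. A plan that expected quitters to be withdrawn could not have been sized this way.

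**5. What bias would follow if the reason were used.** Let a share f of quitters and a share g of non-quitters be withdrawn before Week 12 and dropped from the analysis. All shares are illustrative; the documents give none.

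Observed rate = p(1 − f) / [p(1 − f) + (1 − p)(1 − g)]

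| f | g | Sham (p = 0.40) | Active (p = 0.70) |
|---|---|---|---|
| 0.10 | 0 | 0.36/0.96 = 37.5% | 0.63/0.93 = 67.7% |
| 0.50 | 0 | 0.20/0.80 = 25.0% | 0.35/0.65 = 53.8% |
| 0.50 | 0.50 | 40% | 70% |
| 0.50 | 0.60 | 0.20/0.44 = 45.5% | 0.35/0.47 = 74.5% |

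Setting g to 0 is not faithful to the literal reading, because a smoker who cuts down below 10 a day also fails the criterion, and reduced consumption is a stated hypothesis. Once those participants count, the rates can fall, stay the same or rise.

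The odds ratio is 3.50 multiplied by the ratio, active over sham, of (1 − f)/(1 − g). With the same f and g in both arms it stays at 3.50. With g = 0, shares f of 25% in sham and 50% in active give 3.50 × 0.50/0.75 = 2.33; reversed, 3.50 × 0.75/0.50 = 5.25. Those shifts need unequal shares that nothing in the plan suggests, and blinding works against them.

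**6. Timing and model.** A participant found abstinent at the Week 12 assessment has already supplied the primary outcome; withdrawal then costs only Week 26 data. Step 5 is also a complete-case calculation. In the planned mixed model, a quitter withdrawn after Week 4 still contributes an abstinent Week 4 value through the subject intercept.

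**The case for a change.** The best argument for rewording is that the reason has little other content. Among the inclusion measures, only CO, cigarettes per day and FTND are repeated during the study, and all three are secondary outcomes that the trial hopes to lower. Seizure history, cardiovascular disease and pregnancy are exclusion criteria, and pregnancy has its own withdrawal item. So the reason is hard to explain as a safety rule. Withdrawal is optional, but replacement after it is not worded as optional. If the reason were used for quitters before Week 12, the missingness would depend on the outcome in a way the model's covariates do not capture. A clarifying sentence would be cheap.

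The textual part of this stands: no exemption is written, and the words taken alone allow the misreading. The consequence does not follow. Nothing in the plan tells staff to compare on-study CO or diary readings with the entry thresholds, and withdrawing quitters would defeat the outcomes those staff are asked to collect. The replacement rule, the optional use of data and the silence on later outcomes apply equally to all seven reasons, so they add no weight to this one. A sentence requiring abstinence data at Weeks 4, 12 and 26 whatever the smoking status would repeat assessments already scheduled without any such condition.

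**Conclusion.** This is a clerical looseness. The first withdrawal reason does not say which inclusion criteria apply after entry and, read alone, conflicts with the abstinence outcomes. Taken as a whole, the protocol judges eligibility at screening and follows quitters to Week 26, so the expected number withdrawn for quitting is none and the expected effect on the Week 12 contrast is nil. The 55% figure is the reach of the literal wording, not a forecast, and the direction of any bias under that wording is undetermined.

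The conclusion assumes that site staff read the withdrawal list alongside the visit schedule and outcome definitions. It would need another look only if withdrawal records showed this reason applied to participants who had quit or cut down. The eligibility and withdrawal sections can be reconciled in passing if the document is reopened for another purpose; which clinical withdrawal rules apply is for the investigators. Neither the design nor the analysis depends on it.

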FTND, Columbia Suicide Severity Rating Scale (C-SSRS), T-QSU, and MNSW will be done once a week. In the event that a participant misses a session during this time where these assessments were intended to occur, they will be conducted at the following visit. Participants are intended to receive 20 TMS sessions, however, any missed TMS sessions (whether due to the participant or to holiday closure of the Temerty centre) will not be rescheduled.

During the follow up visits (i.e., sessions 22-31), in the event a subject misses a session; they will be able to reschedule the session within the same week. If they are not able to attend within the same scheduled week, the session will be considered as a missed session. The following visits will proceed as scheduled.

*COVID-19:*

All participants will be screened for COVID-19 symptoms and COVID-19 contacts. If a participant screens positive, they will not continue treatment at that time and the case will be reviewed with Infection Prevention and Control Canada (IPAC) around if, and when, treatment can resume. IPAC recommendations include that all patients and staff wear surgical masks while at CAMH (including waiting areas).

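### Participants withdrawn during the TMS weeks have no planned later assessment, so anyone withdrawn before the end of Week 4 contributes nothing to the primary Week 12 comparison

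*Combined protocol and SAP*

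**What the plan says.** Termination of the Study introduces its list with "Reasons for withdrawing individual subjects from the study may include one or more of the following". The list includes severe side effects of stimulation and "The subject missed more than 3 days of TMS treatment during the treatment trial period", with holiday closures and COVID excepted. It continues: "When participants are prematurely withdrawn they will be replaced by a new participant until the total recruitment aims are met". On data it says only: "Data collected until the time of withdrawal may be used in analyses".

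The text after the Summary of Events table adds that "any missed TMS sessions (whether due to the participant or to holiday closure of the Temerty centre) will not be rescheduled". The rescheduling rules there concern missed visits by people still in the study, not people who have been withdrawn.

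Stimulation runs in Weeks 1 to 4. Study Design places the cotinine-verified abstinence assessments at the ends of Weeks 4, 12 and 26. Four blood draws are planned in all, including screening, so there is no verified outcome before the end of Week 4.

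Data Analysis specifies "Mixed effect logistic regression that uses abstinence at 4, 12 and 26 weeks as dependent variables", fitted by maximum likelihood under missing at random (MAR), with the primary hypothesis tested by the Week 12 contrast. It adds that "Baseline variables correlated with missingness and/or known to be associated with the outcome will be added as covariates", and that subjects with missing outcomes will be compared with completers "if at least 10 subjects (20%) are found to be missing". It names no analysis population and plans no sensitivity analysis for missing Week 12 abstinence.

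**The concern.** Two of the listed reasons are tied directly to the randomised intervention and can occur only while stimulation is being given. Anyone withdrawn for them before the end of Week 4 leaves before the first outcome the primary model can use. Likelihood estimation under MAR draws on a participant's observed outcomes; with none, that participant is in effect excluded.

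If those lost early are more likely to be smoking, and more are lost from one arm, the remaining groups are no longer the randomised groups and the Week 12 contrast shifts. The planned 95% confidence intervals would not reveal this, because the whole interval moves with the estimate. Replacement restores the number of participants, not the comparability of the arms. Outcomes that were never collected cannot be recovered at analysis.

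The gap is confined to early withdrawals. Anyone with at least one abstinence outcome stays in the model, and later dropout that observed outcomes explain is handled under MAR.

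**Working it through.** **1. The plan's own figures.** Sample Size and Power Calculation assumes 40% abstinence on varenicline, a 30-point difference, α = 0.05 and power 0.80. The two-sided pooled normal formula for 0.40 v 0.70 gives 42 per arm, as stated. The attrition allowance is also consistent: 25/(1 − 1/6) = 30 per arm, or 10 of 60 lost (16.7%). The plan does not say when or in which arm those losses occur.

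**2. Does a participant without outcomes inform the model?** A random-intercept logistic model (group by time) was fitted to 60 simulated subjects, 10 of them with no value at any of the three times, and refitted without those 10. Both fits gave log-likelihood −87.8398 and the same coefficients to five decimals. Such a participant contributes nothing.

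**3. Illustrated bias with no true effect.** The 40% rate and 30 per arm come from the plan; the splits and smoking status are assumptions. With w withdrawn early and a the proportion abstinent among them:

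observed rate = (30 × 0.40 − w × a) / (30 − w)

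| Withdrawn early, active v sham | a = 0 | a = 0.20 |
|---|---|---|
| 2 v 1 | 12/28 − 12/29 = +1.5 points | 11.6/28 − 11.8/29 = +0.7 |
| 3 v 2 | 12/27 − 12/28 = +1.6 | 11.4/27 − 11.6/28 = +0.8 |
| 3 v 1 | 12/27 − 12/29 = +3.1 | 11.4/27 − 11.8/29 = +1.5 |
| 5 v 0 | 12/25 − 12/30 = +8.0 | 11/25 − 12/30 = +4.0 |
| 8 v 2 | 12/22 − 12/28 = +11.7 | 10.4/22 − 11.6/28 = +5.8 |

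At a = 0.40, or with equal loss, the difference is zero. The 8 v 2 row is extreme: it puts the whole attrition allowance before Week 4. With 25 randomised per arm and a = 0, 3 v 1 gives 10/22 − 10/24 = +3.8 and 5 v 0 gives 10/20 − 10/25 = +10.0.

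The primary contrast is on the logit scale. As marginal odds ratios the a = 0 cases are (12/15)/(12/17) = 1.13 for 3 v 1, (12/13)/(12/18) = 1.38 for 5 v 0 and (12/10)/(12/16) = 1.60 for 8 v 2.

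**4. Against sampling error.** For 3 v 1 the standard error is √(0.444 × 0.556/27 + 0.414 × 0.586/29) = 0.132; for 25 per arm at 40% it is √(2 × 0.40 × 0.60/25) = 0.139. So 3 v 1 is 3.1/13.2, about a quarter of a standard error.

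**5. False-positive rate of the Week 12 model contrast.** Simulated with 30 per arm, loss among smokers only, no covariates, no replacement, and 2,000 runs per cell (simulation error 0.5 to 0.8 points):

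| Early loss | Random-intercept SD 1.5 | SD 2.5 |
|---|---|---|
| none | 5.0% | 5.6% |
| 3 v 1 | 4.8% | 6.2% |
| 5 v 0 | 10.1% | 9.0% |
| 8 v 2 | 13.9% | 13.9% |

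**6. Do baseline covariates repair it?** Assume a binary covariate held by half the participants (log odds ratio −1.5, abstinence about 50% v 30%).
- If loss depends on the covariate alone, adjustment removes the bias: for 5 v 0, +1.9 to +2.5 becomes 0.0.
- If loss depends on smoking itself, little is removed: 3 v 1 goes from +3.1 to +2.9, and 5 v 0 from +8.0 to between +7.4 and +7.7.
- If loss falls only on smokers with the covariate, 3 v 1 falls to between +2.2 and +2.5, and 5 v 0 to between +5.8 and +6.6.

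The results in steps 5 and 6 also depend on Week 4 and Week 26 abstinence rates, which the plan does not give. They show the pattern, not exact values.

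**The case against.** The strongest reply is that every bias figure rests on an assumed split. In the moderate case, 3 v 1, the shift is small and the false-positive rate does not rise materially. The damaging cases need truly unequal loss: if withdrawal were equally likely in both arms, 5 v 0 towards active would be 2.6% of splits of five, and 8 v 2 or worse 4.0% of splits of ten. The sham imitates the sound and scalp sensation of the active coil, which argues against assuming unequal loss. This stands, and it limits what can be said about size.

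Some early loss cannot be prevented. Participants who withdraw consent or are lost to follow-up are beyond any follow-up rule, and their share of early loss is unknown. This also stands.

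Withdrawal is discretionary, later contact is not forbidden, and nothing says a replacement displaces the earlier participant's data. That is true, but without a rule, collection of the primary outcome is left to case-by-case judgement.

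Carbon monoxide and Timeline Follow-Back data are taken at every visit, so an early-withdrawn participant can still inform secondary analyses. These data do not supply Week 12 abstinence, and before the Day 15 quit date they say little about quitting.

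Finally, the trial is described as pilot in nature. It nevertheless tests a primary hypothesis, and with 25 to 30 per arm a handful of people moves the estimate.

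**Conclusion.** The point holds and should be fixed. Confidence is high for the mechanism: the plan permits study withdrawal during the TMS weeks, plans no assessment afterwards, and uses a primary model to which a participant withdrawn before the end of Week 4 contributes nothing. The baseline covariates help only as far as baseline predicts the loss, and the comparison with completers describes the loss without correcting it.

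Neither the size nor the direction of any bias is established. Bias requires early loss that is both related to smoking and unequal between arms, and the documents show neither. On the assumptions above it runs from nothing (equal loss, or 40% abstinent among the withdrawn), through about 3 points for 3 v 1, to about 12 points in the extreme 8 v 2 case. The case for acting now is that the missing outcomes can be collected cheaply during the trial and not at all afterwards.

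**What to change.** Leave the rules for stopping stimulation to the clinical team, but separate them from withdrawal from the study.

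- Keep the scheduled Week 4, 12 and 26 abstinence and cotinine assessments for every randomised participant who still consents.
- State that all randomised participants are analysed as assigned, and that newly enrolled participants are added to those withdrawn, not substituted for them.
- Pre-specify sensitivity analyses for missing Week 12 abstinence over a range of assumed abstinence among the missing, for example 0% to 40%, with missing counted as smoking at one end.
- State that counting missing as smoking is itself biased when loss is unequal and some of the withdrawn are abstinent. The bias is −a × (w₁ − w₀)/30, where w₁ and w₀ are the numbers withdrawn early from active and sham. At a = 0.20 and 0.40 this is −1.3 and −2.7 points for 3 v 1, and −3.3 and −6.7 for 5 v 0.

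The cost is protocol wording and up to three already-scheduled visits for a few participants. It will not recover those who withdraw consent or are lost. Abstinence rates and power may be lower. If 5 of 30 per arm count as smoking, the rates become 25 × 0.70/30 = 58% v 25 × 0.40/30 = 33%, and power is about 0.49. The same pooled formula gives 0.57 for 25 per arm at 70% v 40%; the plan states 0.66 for 25 per arm, which is a separate matter.

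A side point, not part of the bias: reconcile the number randomised, given as 50 in Study Design and the rTMS text but 30 per arm in the sample size section.
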